3.1.1.4. Part 1 Combination Dose Finding

Parts 1C, 1D and 1E, are dose finding safety cohorts for PF-06863135 in combination with lenalidomide, pomalidomide or dexamethasone, respectively. Upon determining the PF-06863135 RP2D/MTD/MAD and route of administration as monotherapy either with or without priming dose in Part 1, Parts 1C, 1D and 1E will be initiated to study the safety of PF-06863135 in combination with lenalidomide, pomalidomide, or dexamethasone. Parts 1C and 1D will be started with PF-06863135 one dose level below the MTD/MAD and escalated one dose level unless the RP2D is below the MTD/MAD in which case the RP2D will be used as the starting dose of PF-06863135. If in Parts 1C, or 1D, the combination is not well tolerated, doses of PF-06863135 may be de-escalated to a lower dose level below the starting dose of PF-06863135 used in combination. Part 1E will be a combination of PF-06863135 at RP2D/MTD/MAD and dexamethasone. If this combination is not well tolerated, Part 2E may not be initiated.

As described in [Section 3.4](#), a dose of 1000 µg/kg SC weekly has been selected as the RP2D for PF-06863135 as a single agent. This single agent RP2D will be administered as a fixed dose of 76 mg (a fixed dose equivalent of 1000 µg/kg; see [Section 1.2.9.4](#) for rationale) following a priming dose of 44 mg (a fixed dose equivalent of 600 µg/kg) administered one week earlier. Similarly, Part 1 combination dose finding (Part 1C and Part 1D) will be

PF-06863135
C1071001
Final Protocol Amendment 9, 28 March 2023

administered as fixed doses for PF-06863135 with maintenance doses started one week after the priming dose; the starting dose is one dose level below the single agent RP2D as described in Table 1:

Table 1. Table of Potential Fixed Dose Levels

| Dose level ^a | Priming Dose (mg) | Maintenace Dose (mg) |
|-------------------------|-------------------|----------------------|
| 0 | 24 | 32 |
| 1 (starting) | 32 | 44 |
| 2 ^b | 44 | 76 |

a. Dose level refers to designated dose levels for Part 1C and Part 1D

b. Designated dose level for Part 1E

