3.4. Recommended Phase 2 Dose (RP2D) Definition

Based on preliminary safety, efficacy, PK, and pharmacodynamics data from Part 1 (monotherapy dose escalation), a dose of 1000 µg/kg SC weekly has been selected as the RP2D for PF-06863135 as a single agent. Briefly, single-agent anti-myeloma activity has been observed at doses \geq 215 µg/kg SC with an acceptable safety profile across all dose levels. The overall response rate (ORR) for the 215, 360, 600, and 1000 µg/kg SC dose levels was 75% (3/4), 75% (3/4), 66.7% (4/6) and 83% (5/6), respectively. In addition, preliminary exposure-efficacy analyses indicated that higher PF-06863135 exposure (average concentration at steady state) may be associated with higher probability of objective response, especially in patients with high baseline soluble BCMA. Overall, the data support 1000 µg/kg SC weekly as a tolerable dose that provides clinical benefit for the majority of patients with relapsed or refractory MM, including those with high baseline soluble BCMA.

Although only Grade 1 or Grade 2 CRS was reported during dose escalation, 2 of 6 patients experienced Grade 1 CRS events that lasted for 9 days with the first dose of 1000 µg/kg. The longest duration of CRS in the 600 µg/kg SC cohort was 4 days, which occurred in 1 patient and was Grade 1. Therefore, Part 1.1 of this study evaluates whether the duration of CRS can be mitigated by a single priming dose of 600 µg/kg given one week prior to 1000 µg/kg maintenance dosing (see [Section 1.2.9.6](#) for rationale). Based on preliminary safety data from Part 1.1, administration of a priming dose (600 µg/kg) reduces duration of CRS associated with subsequent maintenance dosing (1000 µg/kg). Therefore, a priming strategy will be adopted for both PF-06863135 monotherapy and combination therapy in this study as well as other studies.

For monotherapy dosing with PF-06863135, the RP2D of 1000 µg/kg will be administered as a fixed dose of 76 mg SC weekly (see [Section 1.2.9.4](#) for rationale) following a single priming dose of 44 mg (fixed dose equivalent of 600 µg/kg) administered one week before initiation of maintenance dosing.

The combination RP2D for PF-06863135 will be determined separately for each combination therapy.

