5.5.3. Dose Reductions

Following dosing interruption or cycle delay due to toxicity, the PF-06863135 dose may need to be reduced when treatment is resumed.

No specific dose adjustments for PF-06863135 are recommended for Grade 1/2 treatment-related toxicity. However, investigators should always manage their patients according to their medical judgment based on the particular clinical circumstances.

Patients experiencing recurrent and intolerable Grade 2 toxicity may resume dosing at the next lower dose level of PF-06863135 once recovery to Grade ≤ 1 or baseline is achieved.

PF-06863135

C1071001

Final Protocol Amendment 9, 28 March 2023

Dose reduction of PF-06863135 by 1 and, if needed, 2 dose levels will be allowed depending on the type and severity of toxicity encountered. Patients enrolled in the first (0.1 µg/kg) cohort will be allowed 1 dose reduction if required. Patients requiring more than 2 dose reductions (or 1 dose reduction for the first cohort) will be discontinued from the treatment and entered into the follow-up phase, unless otherwise agreed between the investigator and the sponsor. If dose reduction of PF-06863135 is needed for any patient who receives fixed doses of PF-06863135 (Parts 1C, 1D, 1E, 2A, 2C, 2D, 2E), the next dose level of PF-06863135 will be 25% lower than the current dose level (eg, from 32 mg to 24 mg, or from 24 mg to 16 mg). All dose modifications/adjustments must be clearly documented in the patient's source notes and case report form (CRF).

Once a dose has been reduced for a given patient, all subsequent cycles should be administered at that dose level, unless further dose reduction is required. Intrapatient dose re-escalation is not allowed.

Patients experiencing a DLT may resume dosing at the next lower dose level (if applicable) once adequate recovery is achieved. Patients experiencing a DLT of prolonged myelosuppression (>42 days) may not resume treatment even if adequate recovery is achieved. No dose reductions are planned for patients experiencing toxicities other than those listed as DLTs. However, patients experiencing recurrent and intolerable Grade 2 toxicity may resume dosing at the next lower dose level once recovery to Grade ≤1 or baseline is achieved. Patients whose hematologic indices improve prior to meeting the criteria for prolonged myelosuppression >42 days may resume dosing at the next lower dose level or permanently discontinue from treatment at the discretion of the investigator.

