Recommended dose reductions for PF-06863135 are described in Table 5.

Table 5. Dose Modifications for PF-06863135 Product-Related Toxicity and for Peripheral Sensory or Motor Neuropathy***

| Toxicity | Grade 1 | Grade 2 | Grade 3 | Grade 4 |
|--|----------------------------------|----------------------------------|--|--|
| Non-hematologic (excluding peripheral neuropathy-see below) | Continue at the same dose level. | Continue at the same dose level. | Withhold dose until toxicity is Grade ≤1, or has returned to baseline, then reduce the dose by 1 level.* | Permanently discontinue.* |
| Hematologic except for lymphopenia, which is expected as part of PF-06863135 mechanism of action | Continue at the same dose level. | Continue at the same dose level. | Withhold dose until toxicity is Grade ≤2, or has returned to baseline, then resume treatment at the same dose level.** If toxicity reoccurs, dosing may be reduced by 1 dose level. If | Withhold dose until toxicity is Grade ≤2, or has returned to baseline, then reduce the dose by 1 level and resume treatment.** If toxicity reoccurs despite dose reduction, dosing may be reduced by |

PF-06863135
C1071001
Final Protocol Amendment 9, 28 March 2023

Table 5. Dose Modifications for PF-06863135 Product-Related Toxicity and for Peripheral Sensory or Motor Neuropathy***

| Toxicity | Grade 1 | Grade 2 | Grade 3 | Grade 4 |
|--|--|---|--|--|
| | | | 
toxicity reoccurs after a maximum of 2 dose level reductions (1 for patients in first cohort), patient may be permanently discontinued from treatment.
 
For platelets, withhold dose if toxicity $\leq 25,000 \text{ mm}^3$ and re-start when platelets have returned to $\geq 25,000 \text{ mm}^3$ or baseline
 | 1 more dose level. If toxicity reoccurs, patient may be permanently discontinued from treatment. |
| Peripheral sensory or motor neuropathy (all causality) See Section 8.4.4 for recommended work-up. | 
Continue at the same dose level.
 
Continue to monitor the participant for signs of worsening neuropathy
 | 
Withhold dose until resolution to Grade ≤ 1, then resume at a reduced dose level.
 
Continue to monitor the participants for signs of worsening neuropathy.
 
If Grade ≥ 2 neuropathy reoccurs, permanently discontinue elranatamab.
 | Permanently discontinue elranatamab. | Permanently discontinue elranatamab |

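### The 25% fixed-dose reduction rule in Protocol 5.5.3 conflicts with its second example (24 to 16 mg is a 33.3% cut), and the term dose level is used in two ways, so second reductions do not have one stated result.

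*Protocol*

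**What the plan says.** Protocol 5.5.3 (Dose Reductions) first sets how many reductions are possible: "Dose reduction of PF-06863135 by 1 and, if needed, 2 dose levels will be allowed". For fixed dosing it then gives a specific rule, which applies "for any patient who receives fixed doses of PF-06863135 (Parts 1C, 1D, 1E, 2A, 2C, 2D, 2E". Under that rule the next dose is "25% lower than the current dose level (eg, from 32 mg to 24 mg, or from 24 mg to 16 mg".

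Table 5, in the same section, tells sites when to reduce. For Grade 3 non-hematologic toxicity, for example, they withhold and then "reduce the dose by 1 level". The table gives no milligram amount and no percentage.

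The only list of fixed doses is in Section 3.1.1.4, "Table 1. Table of Potential Fixed Dose Levels". Its maintenance doses are 32, 44 and 76 mg for levels 0, 1 and 2, with priming doses of 24, 32 and 44 mg. The row for the Part 1C and 1D starting level reads "1 (starting) | 32 | 44" (level, priming, maintenance). The text above the table describes that starting level as one dose level under the single-agent RP2D. Section 3.4 gives that RP2D: "the RP2D of 1000 µg/kg will be administered as a fixed dose of 76 mg SC weekly". A footnote limits the table: "Dose level refers to designated dose levels for Part 1C and Part 1D". A second footnote assigns level 2 to Part 1E.

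**The concern.** A worked example exists to show staff how to apply a rule. Here one of the two examples does not follow the rule, and it shows what happens after a patient has already gone from 32 to 24 mg. That is a path the protocol permits. Someone who computes from the percentage and someone who copies the pattern of the examples will reach different second reduced doses.

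The term *dose level* adds to the difficulty. In Section 3.1.1.4 one level below 76 mg is 44 mg. In Section 5.5.3 the next level for an individual patient is a percentage step. Table 5 uses the term without saying which is meant. So does the QTcF rule in Section 7.1.5, which restarts patients at the next lowest level.

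What is at stake is uniform dosing of individual patients after toxicity. No sample size, error rate or decision rule depends on it.

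**Working it through.** **Inputs.** The rule (25% below the current dose) and the examples (32 to 24 mg, 24 to 16 mg) are from Protocol 5.5.3. Maintenance doses of 76, 44 and 32 mg are from Table 1 in Section 3.1.1.4. Patient counts are from Section 1.2.3.1.

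**Step 1: do the examples follow the rule?** Cut = (old − new)/old.
- 32 to 24 mg: 8/32 = 25.0%. This reproduces the rule.
- 24 to 16 mg: 8/24 = 33.3%. This does not; the rule gives 0.75 × 24 = 18 mg.

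**Step 2: is there a reading that fits both examples?** If each step is 25% of the original dose, 32 mg falls by 8 mg each time: 32, 24, 16 mg. Both examples then fit as consecutive steps. The text, however, takes the percentage from the current dose. Rounding 18 mg to a multiple of 8 mg would also give 16 mg, but Section 5.5.3 states no rounding rule.

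**Step 3: where do the two percentage readings part?** These are consequences of each reading, not recommendations.

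| Starting maintenance dose | First reduction, either reading | Second, 25% of current dose | Second, 25% of original dose | Difference |
|---|---|---|---|---|
| 76 mg | 57 mg | 0.75 × 57 = 42.75 mg | 76 − 2 × 19 = 38 mg | 4.75 mg |
| 44 mg | 33 mg | 0.75 × 33 = 24.75 mg | 44 − 2 × 11 = 22 mg | 2.75 mg |
| 32 mg | 24 mg | 0.75 × 24 = 18 mg | 32 − 2 × 8 = 16 mg | 2 mg |

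The first reduction is the same on both readings. The second is not.

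**Step 4: how does Table 1 compare?** Its maintenance steps down are (76 − 44)/76 = 42.1% and (44 − 32)/44 = 27.3%. A site that took one level in Table 5 to mean a Table 1 level would go from 76 to 44 mg; the percentage rule gives 57 mg, which is 13 mg higher. Table 1 does not explain the examples either, since 16 mg does not appear in it.

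**Step 5: who is covered?** At the 22 June 2022 cutoff the fixed-dose parts listed had 15 (Part 2A) + 4 (Part 1C) + 9 (Part 1D) = 28 patients, out of 23 + 30 + 20 + 15 + 4 + 9 = 101. Parts 1 and 1.1 are outside the rule's list.

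**The case against.** The strongest reply is that the plan does define the reduction. Section 5.5.3 gives an explicit formula for every fixed-dose part, and Table 5 sits in the same section, so one level can be read as the 25% step. That stands for a first reduction from 76, 44 or 32 mg. A reader might infer that the reduced dose is left undefined altogether; the documents do not support that.

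The reply continues that Table 1 is a ladder for cohort escalation and de-escalation, limited by its footnotes to Parts 1C, 1D and 1E, and that no section tells a site to take a patient from 76 to 44 mg. This also stands. A reader might infer that the 42.1% step contradicts the 25% rule; it does not, because one concerns cohorts and the other individual patients. What remains is a risk of wording: the protocol itself places 44 mg one dose level under 76 mg, and neither Section 5.5.3 nor Table 5 says that this usage does not apply.

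Third, the reach of the faulty example is narrow. A maintenance dose of exactly 24 mg arises under the rule only after a first reduction from 32 mg, the level below the combination starting level, and the documents do not say that anyone was treated there. That is fair for the example taken literally. But a site that infers the constant-step pattern from the examples would differ from the rule at the second reduction from 76 or 44 mg too.

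Last, a reader might infer that the dose summaries would be wrong. That is weak. Under SAP 6.2.1 the administered dose is the sum of the recorded doses, set against a planned dose that does not depend on the reduction. SAP 8.2.3.5 counts reductions and lists them as yes or no.

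**Conclusion.** The contradiction between the rule and its second example is certain: 33.3% against a stated 25%, or 16 against 18 mg. It lies on a permitted path, so it is more than a typing slip. Its practical size is a gap of 4.75, 2.75 or 2 mg at the second reduction from 76, 44 or 32 mg, assuming that sites follow either the stated percentage or the constant-step pattern. The double use of *dose level* is a secondary problem of wording. It could produce a 13 mg difference at the first reduction from 76 mg, but only if a site applied the cohort table to an individual patient.

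The matter is limited to the fixed-dose parts, 28 of 101 patients at the cutoff. A reader might take it to affect everyone still on treatment. The rule's scope does not support that, and the documents do not say how many of the 28 remain on treatment. Enrollment is complete, but Section 3.1 allows treatment up to about 30 months after the last patient's first dose, so reductions may still occur.

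**What to change.** The sponsor should:
- reconcile the 25% rule in Section 5.5.3 with its second example, stating whether the percentage is taken from the current or the original dose, and how fractional results such as 42.75 mg are handled;
- state in Table 5, and in Section 7.1.5 where the same term is used, whether a dose level for a patient on fixed dosing means the Section 5.5.3 step or a Table 1 level.

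The result should be one stated dose for each first and second reduction. Which doses those are is for the sponsor's clinical team; none is proposed here.

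The cost is a protocol clarification letter or a few lines in the next amendment. The SAP needs no change.

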3.2. Dose Limiting Toxicity (DLT) Definition

Monitoring for DLTs will occur during Part 1. Severity of adverse events (AEs) will be graded according to National Cancer Institute Common Terminology Criteria for Adverse Events (CTCAE) version 4.03. The severity of cytokine release syndrome (CRS) will be assessed according to the grading described by Lee et al. (2014 and 2019,^{2,3} See [Appendix 5](#)). For the purpose of dose escalation, the DLT observation period will be up to the end of Cycle 1 in each patient. For those patients receiving a priming dose, Cycle 0 and Cycle 1 would be included in the DLT observation period. DLT evaluable patients will include patients that have experienced a DLT in the DLT observation period or. DLT evaluable patients will also include those who received all of their planned doses of PF-06863135 in the initial DLT observation period if Q2W dosing is being evaluated or at least all but one of their planned doses of PF-0686135 if Q1W dosing is being evaluated, provided a dose was not missed due to toxicity attributed to study drug. Safety information from any patients that do not meet DLT evaluable criteria could still be considered for overall dose escalation decisions although they would not factor into mTPI decision rules.

Any of the following adverse events observed within the DLT observation period considered related to PF-06863135 or PF-06863135 in combination with lenalidomide, pomalidomide, dexamethasone, will be classified as DLTs:

Hematological:

- Grade 4 neutropenia lasting >5 days. Except in lenalidomide combination cohort where it can be managed by dose reduction of lenalidomide in the next cycle.
- Febrile neutropenia (defined as an absolute neutrophil count [ANC] <1000/mm³ with a single temperature of >38.3°C [101°F], or a sustained temperature of ≥38°C [100.4°F] for more than one hour). If fever is determined to be a symptom of CRS confirmed by clinical course and cytokine levels and resolves in a manner consistent with CRS, this would no longer be considered a DLT, and the patient may resume treatment.
- Grade ≥3 neutropenia with infection.
- Grade 4 thrombocytopenia (unless the study entry baseline count was ≥25,000 and <50,000 to take into account bone marrow suppression due to multiple myeloma, in

PF-06863135

C1071001

Final Protocol Amendment 9, 28 March 2023

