this case grade 4 thrombocytopenia needs to be accompanied by \geq Grade 2 bleeding to be a DLT). For subjects who experience a platelet count $<10,000/\text{mm}^3$, this is considered a DLT irrespective of other factors with the exception of lenalidomide-related Grade 4 thrombocytopenia manageable by platelet transfusions and lenalidomide dose reduction in the next cycle.

- Grade 3 thrombocytopenia with \geq Grade 2 bleeding.

Non-hematological:

- Grade 4 Adverse Events (AEs).
- Grade 3 AE lasting ≥ 5 days despite optimal supportive care, with the exception of AE attributed to a CRS event (ie, Grade 3 transaminitis).
- Grade 3 CRS, except those CRS that have i) not been maximally treated (ie, lack of administration of standard of care treatment per the institution's, Investigator's, or treating physician's guidelines for the management of CRS) or ii) improved to \leq Grade 1 within 48 hours.
- Grade 4 CRS.
- Confirmed drug-induced liver injury (DILI) meeting Hy's law criteria outlined in [Section 8.4.1](#).
- Grade 4 laboratory abnormalities deemed clinically significant by the investigator shall be reported as Grade 4 AE as described in [Section 8.2.2](#).
- Clinically important or persistent toxicities (eg, toxicities responsible for significant dose delay) that are not included in the above criteria may also be considered a DLT following review by the investigators and the Sponsor. All DLTs need to represent a clinically significant shift from baseline.

The following AEs will not be adjudicated as DLTs:

- Isolated Grade 3 laboratory abnormalities that are not associated with clinical sequelae and are corrected with supplementation/appropriate management within 72 hours of their onset or deemed clinically insignificant by the investigator.

PF-06863135
C1071001
Final Protocol Amendment 9, 28 March 2023

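### Protocol 5.5.3 plans no dose reductions for toxicities that are not DLTs, yet Table 5 in the same section reduces by grade: a clear conflict for short Grade 3 non-hematologic events, a partial one for short Grade 4 neutropenia

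*Protocol*

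**What the plan says.** Three parts of the protocol bear on the dose at which a patient restarts after a toxicity.

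- **Section 5.5.3, narrative.** A patient with a DLT may restart one level down. Then: "No dose reductions are planned for patients experiencing toxicities other than those listed as DLTs". Recurrent, intolerable Grade 2 toxicity is excepted. A later sentence in the same paragraph lets patients whose blood counts recover before 42 days restart one level lower or stop, at the investigator's discretion. Earlier, the section says that one or two reductions are allowed "depending on the type and severity of toxicity encountered". Once made, a reduction is not reversed.
- **Section 5.5.3, Table 5.** The table is organised by grade and never mentions DLTs. For product-related Grade 3 non-hematologic toxicity, the dose is withheld until Grade 1 or lower "or has returned to baseline, then reduce the dose by 1 level". For Grade 4 hematologic toxicity other than lymphopenia, it is withheld until Grade 2 or lower, "then reduce the dose by 1 level and resume treatment".
- **Section 3.2, DLT list.** A Grade 3 non-hematologic event counts only if it lasts at least 5 "days despite optimal supportive care, with the exception of AE attributed to a CRS event". Neutropenia counts as "Grade 4 neutropenia lasting >5 days", or when it comes with fever or infection. Expressly not DLTs: "Isolated Grade 3 laboratory abnormalities that are not associated with clinical sequelae and are corrected with supplementation/appropriate management within 72 hours". A catch-all adds that important or persistent toxicities "that are not included in the above criteria may also be considered a DLT following review by the investigators and the Sponsor".

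Sections 5.5.1 and 5.5.2 both refer the restart-dose decision to 5.5.3. Nothing says whether its text or its table governs.

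**The concern.** Section 5.5.1 interrupts treatment for potentially related Grade 3 or 4 toxicity, so a restart dose must be chosen for exactly the events on which 5.5.3 disagrees with itself. One site could follow the sentence and resume at full dose; another could follow Table 5 and go down a level for the same event. With re-escalation ruled out, the difference stays with the patient for the remainder of treatment.

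This is a safety-dosing instruction, so consistency matters for its own sake. It also feeds descriptive outputs: SAP Section 8.2.3.5 tabulates patients with dose reductions and percentage of planned dose, and those figures would mix two conventions.

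**Working it through.** The plan gives no figure to reproduce. The check is a comparison of rules, followed by the size of one dose step.

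**Step 1. Compare the rules for each event.**

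| Event (product-related) | On the 3.2 list? | 5.5.3 narrative | Table 5 | Conflict |
|---|---|---|---|---|
| Grade 3 non-hematologic, under 5 days | No, unless the catch-all is used | None planned | Reduce one level | Clear |
| Isolated Grade 3 non-hematologic laboratory value, corrected within 72 hours | Expressly excluded | None planned | Reduce one level | Clear; a subset of the row above |
| Isolated Grade 3 hematologic laboratory value, first episode | Expressly excluded if corrected within 72 hours | None planned | Resume at same level | None |
| Grade 4 neutropenia, 5 days or less, no fever or infection | No, unless the catch-all is used | None planned, or permitted through the blood-count sentence | Reduce one level | Partial |

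Two qualifications apply. Under the Table 5 footnote, nausea, vomiting and diarrhea must persist at Grade 3 or 4 despite maximal therapy before the dose changes. Section 8.2.2 records a laboratory finding as an AE when, for example, it needs medical intervention, so corrected values can come within Table 5.

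**Step 2. Size of one level, fixed dosing.** Inputs: 76 mg (Section 3.4) and a 25% step (Section 5.5.3).

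- Reduced dose: 76 × 0.75 = 57 mg
- Difference per dose: 76 − 57 = 19 mg

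**Step 3. Per 28-day cycle.** Section 1.2.9.5 allows a move to two-weekly or once-per-cycle dosing after at least 6 months on weekly treatment with at least 2 months of stable disease.

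| Schedule | Doses per cycle | Full dose | Reduced dose | Gap |
|---|---|---|---|---|
| Weekly | 4 | 304 mg | 228 mg | 76 mg |
| Two-weekly | 2 | 152 mg | 114 mg | 38 mg |
| Once per cycle | 1 | 76 mg | 57 mg | 19 mg |

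**Step 4. Weight-based dosing.** If the next level below 1000 µg/kg is the 600 µg/kg of Table 3, the step is 1 − 600/1000 = 40%. That choice of level is an assumption.

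**Step 5. Who could be affected.** Amendment 8 (6 June 2021) records enrollment as complete. Amendment 9 is dated 28 March 2023, between 21 and 22 months later. If the last first dose fell by the earlier date, patients still on treatment under Amendment 9 were at least 21 months in. With dosing limited to about 30 months after the last patient's first dose, at most about 30 − 21 = 9 months remained. Section 1.2.3.1 reports 101 patients enrolled and 41 on full-dose monotherapy by 22 June 2022. It gives no count still on treatment, and no grade, duration or relatedness for the adverse event rates it lists.

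**The case against.** The best reply is that the intended rule is obvious. The section ties reductions to type and severity of toxicity and introduces Table 5 as the place where they are set out. The history for Amendment 1 attributes the Grade 3 reduction and Grade 4 discontinuation rules for non-hematologic toxicity to FDA guidance. The sentence then looks like a leftover, and saying that reductions are not planned is weaker than forbidding them. All of this stands as evidence of intent. It does not remove a contrary operative sentence, and it is a reason to delete it.

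The catch-all in 3.2 and the investigator–sponsor agreement clause in 5.5.1 soften the conflict in individual cases. Both are discretionary, and neither sets the default.

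The blood-count sentence in 5.5.3 is a real qualification. It is not conditioned on a DLT and can be read to cover short Grade 4 neutropenia. A reader might infer that recurrent Grade 2 toxicity is the only exception in the narrative, and that the neutropenia case is as stark as the Grade 3 case. The text does not support that. The remaining disagreement there is between a direction and a permission.

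Enrollment being complete, and longer dosing intervals being allowed, also limit the practical reach.

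**Conclusion.** The inconsistency is real and should be corrected. It is clear for related Grade 3 non-hematologic toxicity under 5 days and partial for short, uncomplicated Grade 4 neutropenia. A patient on 76 mg would receive 19 mg less per dose under Table 5 than under the sentence, for as long as treatment continues. This assumes that the stated 25% step applies and that the site follows one reading literally.

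Three stronger readings are tempting but unsupported:

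- A reader might count corrected Grade 3 laboratory abnormalities as a further, separate conflict. They are part of the short Grade 3 group, and only non-hematologic tests conflict.
- A reader might take the weekly gap of 76 mg per cycle as typical. It is the upper case for long-treated patients on 76 mg, who may be on longer intervals.
- A reader might infer that DLT counts, the MTD or the RP2D are compromised. The conflict concerns the dose after an event, not whether the event is a DLT, and nothing in the documents shows an effect on dose finding, sample size or an SAP analysis rule.

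How many patients are affected cannot be worked out from the documents.

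**What to change.** In Section 5.5.3, replace the sentence with: *Reductions for toxicities that are not DLTs follow Table 5.* Add that Table 5 prevails wherever text and table differ.

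Two conforming edits belong with it:

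- The sentence recommending no specific adjustment for Grade 1/2 toxicity should except peripheral neuropathy, since Table 5 resumes at a reduced level after Grade 2 neuropathy.
- The sentence allowing patients with a DLT to restart one level down should except cases where Table 5 directs permanent discontinuation, such as Grade 4 non-hematologic toxicity.

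Table 5 itself should stay as it is. An exception for briefly abnormal Grade 3 laboratory values is not needed to resolve the conflict, and would loosen a criterion that the amendment history ties to regulatory advice.

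The drafting cost is a few lines. As a protocol change it needs the ethics review described in Section 12.1, so it fits best in the next amendment, with a short clarification to sites that still have patients on treatment. No analysis or data collection changes.
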